7.2.3 Immediate Reporting of Adverse Events to the Sponsor

7.2.3.1 Serious Adverse Events

A serious adverse event is any adverse event occurring at any dose or during any use of Sponsor's product that:

- Results in death;
- Is life threatening;
- Results in persistent or significant disability/incapacity;
- Results in or prolongs an existing inpatient hospitalization;
- Is a congenital anomaly/birth defect;
- Is an other important medical event.

Note: In addition to the above criteria, adverse events meeting either of the below criteria, although not serious per ICH definition, are reportable to the Sponsor in the same timeframe as SAEs to meet certain local requirements.

- Is a cancer;
- Is associated with an overdose.

Refer to [Table 6](#) for additional details regarding each of the above criteria.

For the time period beginning when the consent form is signed until treatment allocation/randomization, any serious adverse event, or follow up to a serious adverse event, including death due to any cause, that occurs to any subject must be reported within 24 hours to the Sponsor if it causes the subject to be excluded from the trial, or is the result of a protocol-specified intervention, including but not limited to washout or discontinuation of usual therapy, diet, placebo treatment or a procedure.

For the time period beginning at treatment allocation/randomization through 14 days following cessation of treatment, any serious adverse event, or follow up to a serious adverse event, including death due to any cause, whether or not related to the Sponsor's product, must be reported within 24 hours to the Sponsor either by electronic media or paper. Electronic reporting procedures can be found in the EDC data entry guidelines. Paper reporting procedures can be found in the Investigator Trial File Binder (or equivalent).

Additionally, any serious adverse event, considered by an investigator who is a qualified physician to be related to the Sponsor's product that is brought to the attention of the investigator at any time outside of the time period specified in the previous paragraph also must be reported immediately to the Sponsor.

All subjects with serious adverse events must be followed up for outcome.

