7.2.3.3 Protocol-Specific Exceptions to Serious Adverse Event Reporting

Potential pre-specified efficacy endpoints will be submitted for adjudication to an independent CEC (see Section 7.3.4). This will include all-cause mortality, including cardiovascular and non-cardiovascular death.

The following events will not be subject to expedited reporting/unblinding by the Sponsor to investigators, Ethics Committees/IRBs, and regulatory agencies, regardless of causality, unless and until the event is reviewed by the CEC and found not to meet the specified criteria in the CEC charter for the following endpoint types:

- Cardiovascular Death
- Cardiovascular hospitalizations
- Urgent Heart Failure Visit

Fatal events that are adjudicated to be non-cardiovascular deaths by the CEC will require an independent Merck company causality assessment and will be subject to expedited reporting, where required by local legislation, when there is evidence suggesting a causal relationship between vericiguat and the event.

If an event submitted for adjudication is determined by the CEC not to meet the endpoint criteria in the CEC charter, the event will then be subject to expedited reporting (as appropriate, based upon both investigator and Merck company causality assessment of drug relationship, as required by local legislation).

Note that all of these events, including confirmed adjudicated cardiovascular events, will be reviewed and monitored by an external DSMB unblinded to treatment as part of the overall assessment of safety and efficacy for vericiguat. Based upon their regular review of unblinded safety results, the DSMB is empowered by the DSMB charter to make recommendations with regard to trial conduct to assure the continuing appropriate safety of the subjects participating in the study.

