8.6.2 Statistical Methods for Safety Analyses

Safety and tolerability will be assessed by clinical review of all relevant parameters including adverse events (AEs), laboratory tests, and vital signs.

The analysis of safety results will follow a tiered approach (Table 8). The tiers differ with respect to the analyses that will be performed. Safety parameters or adverse events of special interest that are identified a priori constitute “Tier 1” safety endpoints that will be subject to inferential testing for statistical significance with p-values and 95% confidence intervals provided for between-group comparisons. Other safety parameters will be considered Tier 2 or Tier 3. Tier 2 parameters will be assessed via point estimates with 95% confidence intervals provided for between-group comparisons; only point estimates by treatment group are provided for Tier 3 safety parameters. P-values (Tier 1 only) and 95% confidence intervals (Tier 1 and Tier 2) will be provided for between-treatment differences in the percentage of subjects with events; these analyses will be performed using the unstratified Miettinen and Nurminen method.

Adverse events (specific terms as well as system organ class terms) and predefined limits of change in laboratory and vital signs that are not pre-specified as Tier-1 endpoints will be classified as belonging to "Tier 2" or "Tier 3", based on the number of events observed.

Membership in Tier 2 requires that at least 4 subjects in at least one treatment group exhibit the event; all other adverse events and predefined limits of change will belong to Tier 3.

The threshold of at least 4 events was chosen because the 95% confidence interval for the between-group difference in percent incidence will always include zero when treatment groups of equal size each have less than 4 events and thus would add little to the interpretation of potentially meaningful differences. Because many 95% confidence intervals may be provided without adjustment for multiplicity, the confidence intervals should be regarded as a helpful descriptive measure to be used in review, not a formal method for assessing the statistical significance of the between-group differences in adverse events and predefined limits of change.

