Continuous measures such as changes from baseline in laboratory and vital signs that are not pre-specified as Tier-1 endpoints will be considered Tier 3 safety parameters. Summary statistics for baseline, on-treatment, and change from baseline values will be provided by treatment group in table format. In addition, summary statistics for the difference between treatment groups will also be provided, along with nominal p-values for between-group differences. Mean change from baseline over time will be plotted with the corresponding standard errors.

Table 8 Analysis Strategy for Safety Parameters

Safety Tier	Safety Endpoint [†]	p-Value	95% CI for Treatment Comparison	Descriptive Statistics
Tier 1	
 • Syncope • Symptomatic hypotension 	X	X	X
Tier 2	
 Any AE Any Serious AE Any AE leading to death Any Drug-Related AE Any Serious and Drug-Related AE Discontinuation due to AE Specific AEs, SOCs, or PDLCs[‡] (incidence \geq4 of subjects in one of the treatment groups) 		X	X
Tier 3	
 Specific AEs, SOCs or PDLCs[‡] (incidence $<$4 of subjects in all of the treatment groups) Change from Baseline Results (Labs, Vital Signs) 			X

[†] Adverse Event references refer to both Clinical and Laboratory AEs.
[‡] Includes only those endpoints not pre-specified as Tier 1 or not already pre-specified as Tier-2 endpoints.
 Note: SOC=System Organ Class; PDLC=Pre-Defined Limit of Change; X = results will be provided.

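### As written, the Any Serious AE total in Table 8 (and, less importantly, AE leading to death) includes the trial's own efficacy events, so a diffuse excess of other serious events could read as neutral or favourable

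*Combined protocol and SAP*

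**What the plan says.** Table 8 in section 8.6.2 lists the Tier 2 totals, among them "Any AE Any Serious AE Any AE leading to death". For these, "Tier 2 parameters will be assessed via point estimates with 95% confidence intervals provided for between-group comparisons", and "these analyses will be performed using the unstratified Miettinen and Nurminen method". The only exclusion in the table's footnotes, "Includes only those endpoints not pre-specified as Tier 1 or not already pre-specified as Tier-2 endpoints", stops an item from appearing twice. It does not concern endpoint events.

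Section 7.2 counts a worsening of a pre-existing condition as an adverse event and makes no exception for heart failure. Section 7.2.3.1 makes an event serious if it is fatal or if it "Results in or prolongs an existing inpatient hospitalization". From randomization to 14 days after treatment stops, sites must report "any serious adverse event, or follow up to a serious adverse event, including death due to any cause, whether or not related" (that is, whatever the causal link with study drug).

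Section 7.2.3.3 contains the one exception for endpoint events: "The following events will not be subject to expedited reporting/unblinding by the Sponsor to investigators, Ethics Committees/IRBs, and regulatory agencies, regardless of causality". It governs what the Sponsor sends onward, not what the site records. Section 8.4.3 says that adjudicated endpoint events enter the final efficacy and safety analyses. Its reference to the supplemental SAP covers only adjudicated events that are not already endpoints.

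**The concern.** A row for all serious events lets a reader see harm that is spread over many terms, none of them large enough to stand out alone. In this population many of the serious events will be the HF hospitalizations and CV deaths that the drug is meant to prevent. If vericiguat works as assumed, the row favours vericiguat because of efficacy already credited in the primary analysis. An excess of other serious events then has to exceed that credit before the total shows any excess at all. Safety and tolerability is secondary objective 6, and the plan has no overall row for serious events other than endpoints.

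**Working it through.** **Inputs from section 8.9.** 4872 subjects, 1:1, so 2436 per arm; placebo 12-month rates of 11% (CV death) and 23% (composite); hazard ratio (HR) 0.8; 10% per year stop treatment and move to the placebo hazard; 2% per year are lost; 30 months' accrual with a 12-month ramp, plus 9 months; final one-sided alpha 0.0242. The adverse event window (on treatment plus 14 days) is from section 7.2.3.1.

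**The plan's own figures first.** Without dilution, events needed = 4(z_alpha + z_beta)^2 / (ln HR)^2 = 4(1.974 + 0.842)^2 / (0.2231)^2 = 637. The plan states 782 and says that it allows for dilution. A simulation with exponential hazards and all the inputs above gives:

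| | Plan | Simulated | Diluted HR | Power (plan / simulated) |
|---|---|---|---|---|
| CV deaths | 782 | 774 | 0.816 | 80% / 80.2% |
| Primary events | 1561 | 1545 | 0.818 | about 98% / 97.6% |

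This uses a quadratic accrual rate. A linear ramp gives 810 and 1606 events, with power of 81.1% and 97.9%. The simulated median follow-up (609 days) is longer than the plan's 532 days, so the accrual shape is approximate, but the event counts and power agree.

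**Endpoint events inside the window.** The same model gives 31.5% of placebo and 26.4% of vericiguat subjects with a primary event by 14 days after stopping drug, a difference of -5.1 points.

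**Effect on Any Serious AE.** Let E be the proportion with an endpoint event in the window and q the proportion with another SAE. If the two are independent, total = 1 - (1 - E)(1 - q). The plan gives no value for q, so a range is assumed. Intervals are Miettinen and Nurminen with 2436 per arm.

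| q, placebo (assumed) | Total difference, no true difference in q | Excess in q that brings the total to zero | Total difference, true ratio 1.2 in q |
|---|---|---|---|
| 10% | -4.6 | +6.3 | -3.1 (-5.8 to -0.4) |
| 20% | -4.1 | +5.6 | -1.1 (-3.9 to 1.6) |
| 30% | -3.6 | +4.9 | +0.9 (-1.9 to 3.7) |
| 40% | -3.1 | +4.2 | +2.8 (0.1 to 5.6) |

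Worked case, q = 20% against 24%: placebo total 1 - 0.685 x 0.80 = 45.2%; vericiguat total 1 - 0.736 x 0.76 = 44.1%; difference -1.1. With the endpoint events left out, the same data read +4.0 (1.7 to 6.3).

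**The same question with yearly rates.** A second simulation gives other SAEs a placebo hazard of 10, 15 or 25% per year, adds non-CV death at 2% per year (both assumed), and stops drug at 12% per year. Endpoint events in the window are then about 31% against 26%. With no true difference in other SAEs, Any Serious AE differs by about -4.3, -4.0 and -3.4 points. With 20% more other SAEs on vericiguat, it differs by about -2.6, -1.6 and -0.1. In the middle case, other SAEs alone are 17.8% against 21.2%, or +3.4 points.

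**Fatal events.** CV death in the window is 15.9% against 13.0% in the first model and 15.6% against 12.7% in the second, -2.9 points in both. Causes of death are exclusive, so they add. With assumed non-CV deaths of 3% against 6%, the total is 15.9 + 3 = 18.9% against 13.0 + 6 = 19.0%, or +0.1 (-2.1 to 2.3). Non-CV deaths alone show +3.0 (1.9 to 4.2).

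**The case against.** **Inclusion is inferred.** No sentence says that Table 8 counts endpoint events, section 8.4.3 can be read in more than one way, and the data entry guidelines and the Clinical Events Committee (CEC) charter are not available here. That stands as a caution. The reporting rules still point one way, and nothing in the plan takes the events out.

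**The intervals are descriptive.** Section 8.6.2 says so, and Tier 2 has no p-values. This stands: no decision rule depends on these rows.

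**Other rows would show harm.** Syncope and symptomatic hypotension are tested in Tier 1. Any specific term or system organ class with at least 4 subjects in one arm gets its own interval. There are drug-related rows, and an unblinded DSMB reviews these events. A reader might infer that real harms would go unseen, but the documents do not support that. What remains is an excess spread over many terms, or one in a class that also holds the heart failure terms.

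**Deaths are covered elsewhere.** CV death and all-cause mortality are separate adjudicated intention-to-treat endpoints, so a marked excess of non-CV deaths would be visible by comparing them. This largely answers the point for fatal events.

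**Other totals.** A reader might extend the point to Any AE and Discontinuation due to AE. Section 5.8 continues study drug after non-fatal outcome events, so HF hospitalization should seldom drive discontinuation. For Any AE no shift has been quantified.

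**Excluding endpoints could hide harm.** A reader might conclude that the endpoint-free row should become the basis for judging harm. It should not: if vericiguat raised CV death or HF hospitalization, that row would conceal it.

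**Fewer HF hospitalizations is a real gain.** It is. The difficulty is that the total mixes that gain with other serious events and cannot show the two apart.

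**Conclusion.** The concern holds for Any Serious AE and, with less weight, for AE leading to death. Under the plan's rates, and if vericiguat has the assumed effect, endpoint events alone move Any Serious AE by about 3 to 4.6 points in favour of vericiguat and fatal events by about 2.9 points. The direction follows from the plan's assumptions. The size for Any Serious AE depends on the assumed rate of other SAEs and on their independence from endpoint events. At 10 to 25% per year, a diffuse 20% relative excess reads as about -2.6 to -0.1 points. If other SAEs are more common (30 to 40% of placebo subjects over the trial), the excess is reduced to +0.9 to +2.8 points but not reversed. This is a limit on what a descriptive row can show. It affects no confirmatory test, and it does not mean that the plan as a whole is blind to harm.

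**What to change.** In section 8.6.2 and Table 8, keep the existing all-event rows and add two Tier 2 rows by the same Miettinen and Nurminen method:

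- Any Serious AE excluding CEC-confirmed CV death and HF hospitalization.
- AE leading to death excluding CEC-confirmed CV death (in effect, a non-CV death row).

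State that the two versions are read together and that neither is the sole basis for conclusions on harm. Leave Any AE and Discontinuation due to AE as they are. Adjudication is blinded, so knowledge of the arm cannot influence which events are excluded. Section 7.2.3.3 already requires CEC decisions to be tied to reported events, and section 8.0 lets non-confirmatory changes go into the supplemental SAP before unblinding.

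The cost is a few descriptive rows and no new data. One side effect should be noted beside the table: longer survival on vericiguat gives slightly more time for other SAEs, which adds about 0.3 to 0.7 points to the endpoint-free row with no true difference.

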8.6.3 Summaries of Baseline Characteristics, Demographics, and Other Analyses

The comparability of the treatment groups for each relevant characteristic will be assessed by the use of tables and/or graphs. No statistical hypothesis testing will be performed on these characteristics. The number and percentage of subjects randomized and the primary reason

for discontinuation will be displayed. Demographic variables (e.g., age) and baseline characteristics will be summarized by treatment either by descriptive statistics or categorical tables.

8.7 Interim Analysis

8.7.1 Futility Interim Analysis

A futility interim analysis to assess lack of efficacy is planned at the time when approximately 75% (587) of the planned number of CV death events are observed, and is projected to take place approximately 33 months after the start of the study. The futility analysis, to be performed at the same time as the interim efficacy analysis (see Section 8.7.2, Efficacy Interim Analysis), will be performed with both the primary composite endpoint and CV death. The futility boundary will be based on the point estimate of hazard ratio (vericiguat/placebo). A point estimate of hazard ratio above 0.95 for the primary endpoint and a point estimate of hazard ratio above 1.0 for CV death, simultaneously, will be considered meeting the futility criteria. Based on simulation analysis, the impact of this futility analysis approach on the overall study power is negligible. Under the null hypothesis with true hazard ratio equal to 1 (no treatment effect) for CV death and for the primary endpoint, the probability of stopping the study for futility is approximately 47%. If the true effect size is 20% (hazard ratio of 0.80) as projected for CV death and for the primary endpoint, the probability of stopping for futility is less than 0.1%. An unblinded DSMB will assess the results of the futility interim analysis and may recommend early study termination for futility.

8.7.2 Efficacy Interim Analysis

An efficacy interim analysis is also planned at the same time of futility analysis when approximately 75% of the planned number of CV death events are observed. Based on the assumptions from the sample size calculation, the interim analysis will take place approximately 33 months after start of the study, shortly after all subjects have been accrued. To ensure that the study has accumulated adequate follow up for safety assessment when stopped for positive efficacy results, the timing of the efficacy interim analysis should also ensure that the median follow up time is at least 10 months. Under the assumption of an 11% 12-month placebo event rate for CV death, the median follow-up time when 75% of CV death events have been observed is expected to be approximately 375 days. Approximately 51% of the subjects will have follow-up time of at least 12 months, 38% of at least 15 months, and 26% of at least 18 months. The median treatment duration will be 340 days.

If the observed CV death event rate is substantially higher than anticipated and thus median follow-up time is less than 10 month when 75% of the planned number of CV events has occurred, the efficacy interim analysis will be delayed until 10 months of median follow up is achieved. In this case, the futility analysis will also be delayed and will be performed at the same time as the interim efficacy analysis. Under an extreme scenario of a much higher than anticipated event rate, the efficacy interim analysis may become unnecessary if the timing for the efficacy IA falls too close to the final analysis. The decision to adjust the timing of the efficacy interim analysis or to cancel the efficacy interim analysis under a higher than expected event rate will be made by the blinded Sponsor team.

At the efficacy interim analysis, the primary endpoint and the secondary endpoint of time to CV death will be tested. The study can only be terminated early for success if both the primary endpoint and the CV death endpoint are statistically significant based on the pre-specified interim analysis boundaries. The testing approach controls the overall alpha-level between the primary endpoint and CV death.

The Hwang, Shih and DeCani ($\gamma=6.5$) alpha spending function will be used for the efficacy interim analysis to assess superiority of MK-1242 (vericiguat). The spending function can be expressed as

$$f(t) = \alpha \left(\frac{1 - e^{-\gamma t}}{1 - e^{-\gamma}} \right),$$

with t denoting the percentage of information included at the respective interim analysis.

With this alpha spending approach, the nominal significance level will be approximately 0.0049 (one-sided) at the interim analysis and 0.0242 at the final analysis, respectively. This testing approach controls the one-sided alpha between the efficacy interim analysis and final analysis at 0.025. The corresponding observed hazard ratio for the stopping boundary is approximately 0.81 for CV death at the efficacy interim analysis.

The actual α to be spent at the efficacy interim analysis and final analysis will be precisely determined using the number of actually observed primary outcome events and the alpha spending function defined as above.

At the time of the interim analysis, approximately 587 CV death events and approximately 1171 (may vary depending on the actual event rate) primary endpoint events are expected. A one-sided stratified log-rank test will be used to assess if vericiguat prolongs the time to primary composite endpoint event compared with placebo. The same nominal significance level as used for the primary composite endpoint will also be used for the analysis of the CV death component.

If the study can be stopped early for success, the nominal one-sided significance level of approximately 0.0049 for the primary endpoint and CV death will be applied to other secondary endpoints as well.

If the study cannot be stopped early for success, the CV death component will be analyzed at the final analysis time point as one of the secondary endpoints.

An unblinded DSMB will assess the results of the interim analysis and may recommend early study termination if the interim analysis shows clear and consistent benefit of vericiguat as guided by the above described alpha-spending approach.

If the DSMB recommendation leads to termination of the study at the interim analysis due to efficacy, all subjects will be called in to their final visit. The complete analysis will be based on the entire data collected until the study completion, i.e. it will also include data collected after the cut-off for the interim analysis.

Table 9 summarizes the timing, number of events, endpoint, and the efficacy and futility bounds at each of the interim analysis and at the final analysis.

Table 9 Summaries of the Interim and Final Analyses

Analysis	Key Endpoint(s)	Target Number of Events	Anticipated Time From Study Start	Statistical Testing Criteria
Futility Interim Analysis	Primary Endpoint Time to CV Death	587 CV Death [†] (75% of planned number of events)	Month 33 [†]	A point estimate of HR>0.95 for the primary endpoint and a point estimate of HR>1.0 for CV death for futility
Efficacy Interim Analysis	Primary Endpoint, Time to CV Death	587 CV Deaths [†] (75% of planned number of events)	Month 33 [†]	P<0.0049 (one-sided) on both endpoints for efficacy, corresponding to an observed HR<0.81 for Time to CV Death
Final Analysis	Primary Endpoint, Secondary Endpoints	782 CV deaths [†]	Month 39 [†]	P<0.0242 (one-sided) for statistical significance, using the pre-specified multiplicity adjustment approach (Section 8.8)

[†]Median follow up time of 10 months are also required.

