8.8 Multiplicity Adjustment

The study-wise one-sided alpha level will be controlled at 0.025 for the test of the primary endpoint. Multiplicity due to the interim analysis at 75% of planned CV death events will be controlled using a Hwang, Shih and DeCani ($\gamma=6.5$) alpha spending function as described in section 8.7.

The secondary endpoints will be separated into two families. The first family consists of the components of the primary endpoint, time to CV death and time to first HF hospitalization.

The second family will consist of the endpoints of time to total HF hospitalization, time to all-cause mortality, and time to first occurrence of composite of HF hospitalization or all-cause mortality. The endpoints from the second family will be tested hierarchically and at the same time be adjusted for the interim analysis, thereby maintaining the study-wise alpha level. These secondary endpoints will only be tested if both the primary composite endpoint and CV death are significant at the interim analysis, or if the primary composite endpoint alone is significant at the final analysis. Total HF hospitalization will be tested first, and only if this is significant, the composite of all-cause mortality and HF hospitalization will be tested afterwards. All-cause mortality will be tested only if both of the above endpoints are tested significant (see Figure 2 for the procedure at the final analysis).

At the interim analysis, if the study is stopped early for efficacy due to success on the primary composite endpoint and separately the CV death component, then the HF hospitalization component will be tested at the same alpha level as the CV death component. In addition, the family of secondary endpoints will be tested in a sequential manner using the same alpha as the primary composite endpoint.

[figure not shown]

Figure 2 Testing of Primary and Secondary Endpoints

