8.9 Determination of Sample Size

The sample size estimation is based on a 1:1 randomization and a study-wise one-sided significance level of 0.025. In accordance with the planned interim analysis, the nominal one-sided significance level will be 0.0242 at the final analysis. A conservative approach of power calculation based only on the final analysis is used.

The study will be an event-driven study. It is planned to accrue subjects during 30 months and have a follow-up of 9 months after the last subject is included in the study. This leads to total study duration of 39 months. It is assumed that setting up of all sites will take approximately 12 months, assuming a quadratic ramp-up function for subject accrual.

The primary analysis will be performed in the ITT population. Every effort will be made to follow-up subjects that prematurely stop study medication to collect at least information for the primary endpoint (i.e. information on hospitalizations and death).

It is assumed that 2% of subjects per year will prematurely stop study medication and either object to further follow-up or be lost to follow-up, despite efforts to contact them. In addition, it is assumed that approximately 10% per year of subjects will stop study treatment and can be followed up off treatment for the primary endpoint. When a subject in the placebo group stops treatment prematurely, it is assumed that the hazard for CV death and HF hospitalization does not change, as the subject is expected to continue with standard heart failure therapy. For vericiguat subjects stopping treatment prematurely, it is assumed that they switch to the hazard of the placebo group, as they henceforth will switch back to

standard heart failure therapy. These effects will dilute the observed treatment effect when the ITT analysis approach is used. The sample size calculations are adjusted for this dilution.

The sample size calculation is driven by the CV death component of the composite primary endpoint. For the CV death component, the expected event rate in the comparator group after 12 months is 11%. The relative risk reduction with vericiguat is assumed to be 20%, relating to a HR of 0.8. Using the log-rank test, a sample size of 4872 subjects and a total of 782 CEC confirmed CV deaths will be required to achieve 80% power.

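### The alpha-spending parameter γ=6.5 and the printed formula disagree in sign: as written they spend 0.0248 at the interim, not the stated 0.0049

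*Combined protocol and SAP*

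**What the plan says.** Section 8.7.2 sets one efficacy interim at about 75% of planned CV deaths: "The Hwang, Shih and DeCani ($\gamma=6.5$) alpha spending function will be used for the efficacy interim analysis". It prints the function as f(t) = α(1−e^(−γt))/(1−e^(−γ)), with t the information fraction. Section 8.8 repeats the positive parameter: multiplicity from the interim is "controlled using a Hwang, Shih and DeCani ($\gamma=6.5$) alpha spending function as described in section 8.7".

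Section 8.7.2 then gives the result: "the nominal significance level will be approximately 0.0049 (one-sided) at the interim analysis and 0.0242 at the final analysis, respectively". Table 9 repeats it as "P<0.0049 (one-sided) on both endpoints for efficacy, corresponding to an observed HR<0.81 for Time to CV Death". Section 8.9 bases power on the same final level: "In accordance with the planned interim analysis, the nominal one-sided significance level will be 0.0242 at the final analysis".

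Two further rules matter. The alpha actually spent will be "precisely determined using the number of actually observed primary outcome events and the alpha spending function defined as above". On stopping, "The study can only be terminated early for success if both the primary endpoint and the CV death endpoint are statistically significant".

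**The concern.** In this parameterisation a positive γ spends alpha early and a negative γ spends it late. A value of +6.5 would use nearly the whole 0.025 by 75% information. The stated levels are those of a design that spends late: a strict interim, and a final level close to 0.025. The function and the levels cannot both be right.

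The function takes precedence in practice. The levels are described as approximate, and the interim is triggered by CV deaths while alpha is to be calculated from observed primary events, whose number the plan says may vary. Whoever sets the boundary on the day has to evaluate the function. If they evaluate it as printed, the trial could stop on weaker evidence than Table 9 allows. If it continues, the final analysis must meet a far stricter level than the one behind the sample size.

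**Working it through.** **Inputs.** One-sided α = 0.025, 1:1 allocation, 782 CV deaths and 1561 primary events at the final analysis (Section 8.9). 587 CV deaths and 1171 primary events at the interim, γ = 6.5 and the formula (Section 8.7.2). Information fractions: 587/782 = 0.7506 and 1171/1561 = 0.7502. I use t = 0.75; the other two give the same results to the plan's rounding.

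**Step 1: interim alpha.**

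- γ = +6.5: 0.025 × (1 − e^(−4.875))/(1 − e^(−6.5)) = 0.025 × 0.99236/0.99850 = 0.02485, leaving 0.00015.
- γ = −6.5: 0.025 × (e^(4.875) − 1)/(e^(6.5) − 1) = 0.025 × 129.97/664.14 = 0.00489, leaving 0.02011.

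The plan's 0.0049 is reproduced only by the second. At t = 587/782, a level that rounds to 0.0049 needs γ between about −6.55 and −6.47, so −6.5 is the only one-decimal value that fits. With +6.5, a spend of 0.0049 would need t of about 0.034.

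**Step 2: final level.** Solve P(Z1 < c1, Z2 > c2) = 0.025 − f(0.75), where corr(Z1, Z2) = √0.75.

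- γ = +6.5: c1 = 1.963, c2 = 2.874, nominal level 0.0020.
- γ = −6.5: c1 = 2.583, c2 = 1.974, nominal level 0.0242.

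**Step 3: hazard ratio boundaries**, from HR = exp(−2z/√events). For example, CV death at the interim: exp(−2 × 1.963/√587) = 0.850 and exp(−2 × 2.583/√587) = 0.808.

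| Quantity | Plan states | γ = +6.5 (as printed) | γ = −6.5 |
|---|---|---|---|
| Interim level | 0.0049 | 0.0248 | 0.0049 |
| Final nominal level | 0.0242 | 0.0020 | 0.0242 |
| CV-death HR, interim (587) | about 0.81 | 0.850 | 0.808 |
| Primary HR, interim (1171) | not stated | 0.892 | 0.860 |
| CV-death HR, final (782) | not stated | 0.814 | 0.868 |
| Primary HR, final (1561) | not stated | 0.865 | 0.905 |

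**Step 4: effect of recalculating when t moves.** With γ = −6.5 the interim level is 0.0035, 0.0049 and 0.0068 at t = 0.70, 0.75 and 0.80. With γ = +6.5 it is 0.0248, 0.0248 and 0.0249. The recalculation the plan calls for is therefore a real adjustment under the intended function, and under the printed one it returns almost all of the alpha each time.

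**Step 5: type I error for the primary endpoint under the two-endpoint stopping rule.** Simulated with 4 million draws per correlation. The correlation between the two test statistics is not in the plan; I assumed 0.3, 0.5 and 0.7.

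- +6.5 at both looks: 0.004, 0.006, 0.009.
- −6.5 at both looks: 0.024 at all three.
- 0.0248 at the interim mixed with 0.0242 at the final: 0.025, 0.026, 0.028.

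**Step 6: stopping and power.** These need a diluted true HR, which the plan does not state. Back-solving from 80% power at 782 deaths and level 0.0242 gives exp(−2 × (1.974 + 0.842)/√782) = 0.8176, applied here to both endpoints. Under the two-endpoint rule with correlations 0.3 to 0.7:

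| Quantity | γ = +6.5 | γ = −6.5 |
|---|---|---|
| Chance of stopping early | 65–67% | 39–43% |
| Overall power, primary | 90–91% | 98% |
| Overall power, CV death | 67–69% | 79–80% |

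Section 8.9 counts power at the final analysis only. On that basis a final level of 0.0020 gives about 48% for CV death instead of 80%.

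**The case against.** The strongest reply is that the intent is plain. The numerical levels appear consistently in Sections 8.7.2 and 8.9 and in Table 9, early stopping is tied to pre-specified boundaries, and the text straight after the formula gives 0.0049 as its result. A recalculation that returned 0.0248 beside a tabulated 0.0049 would probably be noticed, so the reference to the function might be read as fine-tuning only. That is fair on likelihood. It does not settle which text governs, because the plan calls the levels approximate and names the function as the source of the exact ones.

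It is also true that type I error is safe if either version is used at both looks. Error passes 0.025 only if the two versions are mixed, and then only slightly. The stopping and power figures rest on assumptions and should not carry the argument; the levels and boundary hazard ratios come from the plan alone.

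A minus sign could have been lost when the PDF was read, and the source file should be checked. But γ lacks the sign in two separate sections while the minus signs inside the formula survived, so this is unlikely.

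Lastly, the documents show a mismatch in sign between parameter and formula, not which of the two was mistyped. That stands, and either correction is acceptable.

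**Conclusion.** The concern holds. The printed function gives 0.0248, 0.0020 and HR 0.850; the plan states 0.0049, 0.0242 and about 0.81. Reversing one sign reproduces all three stated figures, so the stated boundaries are right and the function is not. This rests only on the plan's alpha, event counts and 1:1 allocation, with the usual large-sample variance for the log hazard ratio.

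The consequence of following the text literally is an interim threshold about five times more permissive (0.0248/0.0049) and a final level about one-twelfth of the one used for sample size (0.0020/0.0242). It is not a loss of type I error control, provided one function is used throughout. It must be corrected because the pre-specified rule for setting the boundaries is the part that is wrong.

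**What to change.** Write γ = −6.5 in Sections 8.7.2 and 8.8 and keep the printed formula. Equivalently, keep γ = 6.5 and print f(t) = α(1−e^(γt))/(1−e^(γ)). Do one or the other, not both. Leave 0.0049, 0.0242 and HR 0.81 as they are.

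The cost is one sign in two places, or the exponent signs in one formula, with no change to sample size, event targets, boundaries or trial conduct. Section 8.0 requires a protocol amendment for changes to methods tied to the primary or secondary hypotheses. If the correction is treated as such a change, it should go into an amendment before the interim data are unblinded.
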